2.3 Overview

This will be a multi-country case-control study of severe pneumonia in children <5 years of age. The sites where the study will be conducted are projected to be representative of the areas where most of the severe pneumonia cases in children will occur in 2015 and where key interventions that are expected to be widespread from 2015 onwards are already in place.

Sites:

Seven PERCH sites have been selected:

- Johannesburg, South Africa
- Lusaka, Zambia
- Kilifi, Kenya
- Basse, the Gambia
- Bamako, Mali
- Sa Kaeo and Nakhon Phanom, Thailand
- Dhaka, Bangladesh

Estimated Timeline:

Case-control study timeline:

- June 30, 2010 submission of final clinical protocol to BMGF
- July 30, 2010 submission of sub-contract budgets to BMGF
- July-Sept 2010 (3 months) review of final protocol, SOPs, budgets, etc. by BMGF
- Q4 2010 Q2 2011 (3-6 months) contract signing, site staff hiring, training, IRB approvals
- Jan 2011- April 2013 (2 years at each site) enrollment of cases and controls
- April 2013 May 2013 (2 months) final specimen testing, data cleaning, close-out of controls and cases
- June 2013- July 2013 (2 months) final analyses and report writing

Enrollment of Cases and Controls

Cases and controls will be enrolled over a 2 year period at each site, approximately Jan 2011-April 2013. At larger sites where the total number of eligible patients exceeds the desired sample size, sampling of cases will be implemented. Enrollment will reflect the seasonal distribution of pneumonia patients. Controls will be enrolled on approximately a 1:1 basis to cases, with a minimum of 25 controls enrolled per month at each site. An HIV+ control group will also be enrolled at sites with high HIV prevalence.

Figure 1 illustrates how the monthly minimum enrolment of controls provides a stable set of controls in low incidence months, and how, in peak months, the number of controls above the minimum will be added and collected. The shape of the case and control enrolment curves (dark blue and red, respectively) illustrates that a small interval is anticipated between the number of cases enrolled and the collection of controls. This is a function of the expected lag in

adjustment based on observed cases and the communication of this new target figure to the field workers recruiting controls in the community.

[figure not shown]

Figure I. Illustration of case sampling proportional to the case detection rates

Cases:

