PERCH also aims to model the global distribution of pathology to extend the information from the case-control study to regional and global settings. To do this effectively, data are needed to appropriately characterize the epidemiologic setting of the study sites. For example, knowledge of the distribution of risk factors for each site will facilitate site-to-site comparisons of the etiology distribution found by PERCH, will aid the interpretation PERCH's results relative to those from other studies and will inform the regional and global projection models. Knowing the prevalence of risk factors in the population allows calculation of population attributable risk percent. For this purpose, both individual-level and community-level data will be required. For example, background prevalence of known or potential risk factors will be described among controls. In addition, community-level variables, (e.g. pollution levels) will be gathered from existing sources, including national databases. Because these data will be sought from existing databases, we must ensure good comparability between PERCH data and that from existing data sources. Where possible, the design for collecting data and operationalizing variables in PERCH will attempt to match the methods and measures used in these global databases. Where needed, PERCH will develop adjustment factors to bridge data from study sites to existing sources.

3 Key study personnel, sites and participating institutions

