4.2.2 Admission assessment

4.2.2.1 Clinical

PERCH site investigators will collect the clinical variables that are required to define the entry of a case into the study prior to enrolment. Once a child is recruited to the study they will collect clinical specimens to define the etiology of pneumonia. They will also collect clinical and laboratory data that are not specifically related to etiology for the following three reasons:

- 1. Controlling for case mix: The case mix across different PERCH sites is likely to vary considerably by severity and by the prevalence of co-existing illnesses. Because both of these factors can influence the distribution of pathogens, this information is important for interpreting study findings. Geographic variations in etiology may be more attributable to the local mix of presenting cases than to geographic variation in pathogen distributions. The coarse differentiation of cases into two WHO classes, 'severe' and 'very severe' pneumonia, does not provide sufficient resolution to control adequately for variation in severity across sites. Co-existing illnesses also alter the pattern of etiology and the prevalence of coexisting illnesses varies geographically. Known examples include HIV and sickle cell disease, which are defined by laboratory tests, but other important conditions, such as malnutrition, are defined by clinical variables.
- 2. Prediction model of etiology: Through a comprehensive classification of etiology in a large number of cases, PERCH aims to explore whether different clinical or laboratory variables, or combinations of these, are associated with specific etiologies or, more probably, groups of etiologies and to what extent clinical variables can be used in a prediction model of etiology. This will be explored in a multi-variable model using the first half of the clinical data from all sites to define

the model. The second half of the data from each site will be used separately to provide a series of temporal/geographic validation tests of the model. To differentiate severity into finer strata, to classify existing illnesses and to associate the clinical presentation with different etiologies PERCH will collect data on additional clinical signs, beyond those that were collected at the time of enrollment eligibility, and these will be incorporated into the analysis at the end.

3. Risk factors:

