6.3.1 Sample size

The target enrollment sample size was based on a series of power calculations and incorporates the need to capture seasonal variations in risk factors for pneumonia and in disease incidence, as well as the cost of testing each subject enrolled. The sample size calculations permit sufficient power to undertake site-specific analyses with a reasonable degree of precision, to conduct sub-analyses of pooled data while controlling for age, season, and site, and to support the identification of novel pathogens.

Cases: Small sites (Bamako, Thailand) will enroll all eligible cases. At the other large sites, sampling of cases will be implemented to restrict the target number of PERCH cases to 6300.

Controls: The target number of controls is based on a minimum background enrollment rate of 25 per month (i.e., 600 over 2 years per site) combined with a 1:1 case:control ratio when monthly case enrollment exceeds the minimum control background rate. For large sites, we anticipate that the overall case:control ratio will be approximately 1:1. For small sites, the overall ratio is anticipated to be slightly higher. For Lusaka and Soweto (i.e., sites with high HIV prevalence), an additional HIV+ control group will be added assuming a 1:1 ratio with the number of enrolled HIV+ cases.

Table XIV. Target case and control enrollment by site and total					
Site	Cases	Controls			
		Community	HIV+ controls		
		Controls			
Bamako, Mali	700	900			
Basse, The Gambia	700	900			
Sa Kaeo/Nakhon Phanom, Thailand	500	600			
Soweto/Johannesburg, South Africa	1200	800	400		
Dhaka, Bangladesh	1200	1200			
Kilifi, Kenya	1200	1200			
Lusaka, Zambia	800	850	350		
Total	6300	7	200		

While PERCH has set a target of 6300 cases to be enrolled, the number actually available may range from 5000-7000. This is due either to losses in data for analysis or higher than projected numbers of cases consenting at some sites. Losses may result from inability to collect and test all specimens, ineligibility due to severe pneumonia signs resolving upon administration of bronchodilators, changes in procedures over time that result in excluding some cases from analysis, and because some sites may not be prepared to start in Jan 2011 (due to minor site capacity development or IRB processes) and thus may not achieve a full 2 years enrollment before the study ends. To account for these potential losses, a low (70%) estimate is provided below.

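### The etiology prediction model's tests labelled temporal/geographic are temporal tests reported by site; none uses a site that did not help train the model

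*Protocol*

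**What the plan says.** Protocol section 4.2.2.1, item 2, gives the prediction model as one reason for collecting clinical and laboratory data beyond what etiology requires. The aim is exploratory: to see "to what extent clinical variables can be used in a prediction model of etiology". A multivariable model is to be developed "using the first half of the clinical data from all sites to define" it. Validation follows: "The second half of the data from each site will be used separately to provide a series of temporal/geographic validation tests of the model".

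Section 2.3 states that "Seven PERCH sites have been selected" and that "Cases and controls will be enrolled over a 2 year period at each site". Section 6.3.1 uses case sampling at the larger sites to "restrict the target number of PERCH cases to 6300", with site targets in Table XIV.

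No other part of the protocol plans a held-out site, a leave-one-site-out analysis or an external data set for this model. Section 4.2.2.5 mentions the model only as a possible use for breath-sound classifications. Section 6.2, which sets out the analysis by objective, does not cover it.

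**The concern.** The protocol fixes the split and also names what the split is meant to test, so this is not a detail left for later. A geographic validation asks how a model performs in a place that had no part in building it. Here every place that is tested also took part in the building. Its case mix, its background etiology and the way its staff elicit signs have already shaped the coefficients.

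The distinction matters in this study because the protocol expects the sites to differ in ways that bear on etiology. Section 4.2.2.1 says so directly: "Co-existing illnesses also alter the pattern of etiology and the prevalence of coexisting illnesses varies geographically". If the model is later reported as having passed geographic validation at seven sites, a reader would reasonably take it to work at an eighth. The planned tests could not support that.

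**Working it through.** The protocol gives no sample size or performance target for this model, so there is no stated figure to reproduce. The check counts which sites fall in each half and sizes the alternatives.

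**Inputs.** The Table XIV case targets are Mali 700, The Gambia 700, Thailand 500, South Africa 1,200, Bangladesh 1,200, Kenya 1,200 and Zambia 800. Their sum is 700 + 700 + 500 + 1,200 + 1,200 + 1,200 + 800 = 6,300, which matches the stated total. Table XV gives a low case of 70% of target, 4,410 cases.

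**Assumption.** The protocol does not say whether half means half the time or half the cases. Equal halves by case count at every site are assumed below.

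**Step 1: sites in each set.** Development uses 7 of 7 sites. Validation uses the same 7. Unseen sites in validation: 7 − 7 = 0.

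**Step 2: how far each test site trains the model.** Development n = 6,300 / 2 = 3,150. A site's share of development is (site target / 2) / 3,150. For leave-one-site-out, development n is 6,300 − site target with all data, or 3,150 − site target / 2 with first halves only.

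| Site | Planned test set | Share of development | Leave-one-site-out development, all data | Same, first halves only |
|---|---|---|---|---|
| Thailand | 250 | 250/3,150 = 7.9% | 5,800 | 2,900 |
| Mali, The Gambia (each) | 350 | 11.1% | 5,600 | 2,800 |
| Zambia | 400 | 12.7% | 5,500 | 2,750 |
| South Africa, Bangladesh, Kenya (each) | 600 | 600/3,150 = 19.0% | 5,100 | 2,550 |

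With all data, leave-one-site-out therefore develops on 5,100/6,300 = 81% to 5,800/6,300 = 92% of the cases and tests on 500 to 1,200.

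**Step 3: the low-enrollment case.** At 70% of target, planned development falls to 4,410 / 2 = 2,205 and the site test sets to 175 to 420. Leave-one-site-out on first halves would develop on 1,785 to 2,030.

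**Step 4: expected differences between sites.** From Tables XIV and XVI, projected HIV-positive cases are 84/1,200 = 7% in Kilifi, 63/700 = 9% in Bamako, 400/1,200 = 33% in Soweto and 400/800 = 50% in Lusaka. In the severity target table of section 6.3.1, the very severe share runs from 100/500 = 20% in Thailand to 400/800 = 50% in Lusaka. With differences of this size, good performance at sites already in the model says little about a new one.

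The amount by which the planned tests would flatter performance at a new site cannot be calculated from the protocol.

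**The case against.** The strongest reply is that the label can be read as later in time, broken down by place. On that reading the split does what it says and the defect is loose wording. Testing one pooled model separately at each site does carry geographic information: it shows whether discrimination and calibration differ among the seven locations. Between 81% and 92% of what trains the model comes from sites other than the one being tested. This stands, and a reader who inferred that the tests say nothing about geography, or that transportability is not tested at all, would be going too far. Transport over time is tested at every site. Only transport to a new site is not.

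Three other strong readings also fail. First, a reader might infer that half the cases are thrown away. They are reserved for testing, as any temporal validation requires, and nothing in the protocol prevents a final refit on all the data. Second, a reader might link the split to the statement in section 2.4 that "PERCH also aims to model the global distribution of pathology to extend the information from the case-control study to regional and global settings". That passage concerns the etiology distribution, risk factors and projection models, and it does not mention the clinical prediction model. The protocol nowhere claims that this model works across geographies. Third, a reader might take the flaw to reach the main results. The model is exploratory and is not among the objectives in sections 2.1 and 2.2.

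Leave-one-site-out also has a real limitation. Omitting Soweto or Lusaka removes about 400 of 947 projected HIV-positive cases (42%). Omitting Thailand removes the only site with thalassemia testing. Poor performance at an omitted site may then reflect a predictor or etiology that the other six sites barely contain.

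What survives the objection is the core point: no planned test estimates performance at a site outside the training data, and the word geographic invites the reader to think that one does.

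**Conclusion.** The point holds in a limited form. The validation in section 4.2.2.1 is temporal validation reported by site. None of the seven tests uses an unseen site, and each tested site supplies about 8% to 19% of the development cases at target. The count of unseen sites follows directly from the wording. The percentages assume proportional halves; they are the same at 70% of target because every site is scaled equally. No size can be given for any resulting optimism. Severity is minor: the primary etiology analysis is untouched, and the remedy uses data the study will already hold.

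**What to change.** Make two changes to section 4.2.2.1, item 2, or to the analysis plan that implements it.

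1. Describe the first-half/second-half tests as temporal validation, by site, and say whether half refers to time or to number of cases. Keep these tests.
2. Add leave-one-site-out (internal-external) validation. Fit the model on six sites, assess discrimination and calibration on the seventh, and rotate through all seven. Using all data, development runs on 5,100 to 5,800 cases at target. If separation in time is wanted as well, fit on the first halves of six sites (2,550 to 2,900 cases) and test on the second half of the seventh (250 to 600). Refit the final model on all the data.

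The cost is seven more model fits and some wording, with no extra enrollment or data collection. Reported performance may be less favourable. Results should be read cautiously where the omitted site holds much of the support for a predictor or etiology, such as HIV-positive cases in Soweto or Lusaka. If the added analysis is not wanted, the relabelling alone removes the unsupported description but leaves performance at a new site unknown.

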PERCH intends to collect data on risk factors for three different pneumonia-related outcomes: 1) Severe hospitalized pneumonia; i.e. what makes a child more likely than his peers to get admitted with WHO severe or very severe pneumonia, referring to the primary PERCH case definition; these data will be collected from both cases and controls. 2) Severity of pneumonia; i.e., among cases, what makes a child more likely to present with very severe pneumonia compared to severe pneumonia. Another way to look at this is to say 'what are the markers of severity among cases?'. 3) Pneumonia of a specific etiology; i.e. among cases, what makes a child more likely to have a specific type of pneumonia e.g. risks for RSV pneumonia versus pneumococcal pneumonia. Risk factors for severity and for etiology will entail data collected from only the cases at admission and beyond.

Variable	Notes
General	
Temperature (tympanic/axillary)	record as a continuous variable
Vomiting everything	present / absent
Convulsions	present / absent (not type)
Lethargy	present / absent
Unconsciousness	AVPU scale (Alert, Voice, Pain, Unresponsive)
Respiratory system	
Cough	3+ episodes during 15 minute time intervals (not associated with eating or drinking)
Difficulty breathing	Present / absent
Nasal discharge	present / absent
Croup	present / absent
Unable to breastfeed (infants) or drink due to breathlessness	Standard observed attempt at breastfeeding or to take a drink
Respiratory rate	continuous variable
Lower chest wall indrawing	Present / absent
Stridor	distinguish between "calm" and agitated "stridor" (croup)
Grunting	present / absent (not here restricted to young infants)
Nasal flaring	present / absent
Crackles/crepitations	present / absent and extent of disease (bilat) (recording

Table IV. List of symptoms, signs and laboratory tests that may be evaluated at admission

Та	Table IV. List of symptoms, signs and laboratory tests that may be evaluated at admission			
	Variable	Notes		
		sounds using digital stethoscope in some sites)		
	Wheeze	present / absent (recording sounds using digital		
		stethoscope in some sites)		
	wheeze after bronchodilator	present / absent		
	Decreased breath sounds	present / absent		
	Central cyanosis	present / absent		
	Deep breathing	present / absent		
	Head nodding	present / absent		
	Dullness on chest percussion	present / absent		
	URTI Signs (sneezing, rhinorrhea, pulling on ears)	present / absent		
	Clubbing	present / absent (collected at some sites)		

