٦	ehydration			
	Sunken eyes	present / absent		
	Capillary refill time	Seconds (delayed = more than 3 seconds)		
	Skin turgor/elasticity	Time in seconds to return to normal graded: immediate,		
		slow, very slow (>2sec)		
М	Malnutrition			
	Height/length	continuous scale		
	Admission weight	continuous scale		
	Pedal edema	present / absent		
Sh	nock			
5/1	Heart rate	continuous scale		
	Oxygen saturation	continuous scale (oximetry), adjusted for altitude		
	Miscellaneous			
		procent (abcont		
	Jaundice	present / absent		
	Bulging Fontanelle (< 18 months of age)	present / absent		
	Rash	Type: petechial, purpural, measles		
La	boratory			
	Complete Blood Count, including the following:			
	Hemoglobin	continuous scale		
	Peripheral white cell count	continuous scale		
	Differential white cell count	Percentage		
	Platelet count	continuous scale		
	Malaria	rapid test or smears		

Ta	able IV. List of symptoms, signs and laboratory tests that may be evaluated at admission		
	Variable	Notes	
	HIV serology	PCR confirmation in children under 18m; parent may decline HIV testing	
	Sickle Cell Testing	in some African sites only, method may vary by site (PCR, HPLC or gel electrophoresis)	
	Thalassemia	In Thailand only	

Two PERCH sites, South Africa and Zambia, will also initiate voluntary HIV testing for the mothers of PERCH cases. Currently at both sites HIV testing is done routinely as part of antenatal care. These results may be recorded as exposure to HIV on a child's health card ('Road to Health Card' in South Africa and 'Under 5 Care' in Zambia), but are not captured as part of a child's record in PERCH. We propose either asking the mother for documentation of her recent HIV test result or offering her testing if she has not been tested recently. All testing will be done using trained nurses or HIV testing counselors. We will ask for consent to link these results with the child's PERCH data. We believe that knowing the mother's HIV status will be critical in evaluating a child's HIV exposure status at the time of enrollment in to PERCH. It has been shown that, even in the absence of HIV infection in an infant, HIV exposure during the pregnancy and peripartum period can lead to increased risk of severe or very severe pneumonia; we would like to evaluate this risk further.

The counseling and testing process will follow local ethics requirements, and the timing of the consent for a mother's HIV test will be done according to the clinic flow at each site.

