4.4.2 Demographic and risk factors

Demographic and risk factor information will be the same as what is collected for cases. Refer to section 4.2.2.3.

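### Active ascertainment of maternal HIV status is specified only for mothers of cases, so the case-control odds ratio for HIV exposure at South Africa and Zambia is open to differential ascertainment bias

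*Protocol*

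**What the plan says.** Section 4.2.2.1 of the Protocol states that South Africa and Zambia "will also initiate voluntary HIV testing for the mothers of PERCH cases". The method is "asking the mother for documentation of her recent HIV test result or offering her testing if she has not been tested recently", with consent sought to link the result to the child's study data. The section gives the background: "Currently at both sites HIV testing is done routinely as part of antenatal care". Those results may appear on the child's health card, "but are not captured as part of a child's record in PERCH". On the purpose, it notes that exposure without infection may raise the risk of severe or very severe pneumonia and adds "we would like to evaluate this risk further".

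The same section sets out three risk-factor questions. The first asks what makes a child more likely than peers to be admitted with severe or very severe pneumonia, and for it "these data will be collected from both cases and controls". The other two (severity and specific etiology) use data from cases only.

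For controls, section 4.4.2 says: "Demographic and risk factor information will be the same as what is collected for cases". Table VI in section 4.2.2.3 lists the mother's HIV status in pregnancy among the risk factors, with a footnote that some sites may collect only a subset. That section permits, but does not require, review of case and control health records, and maternal HIV is not among its examples. Sections 4.3 to 4.4.3 describe no documentation request or test for mothers of controls.

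**The concern.** Whether HIV exposure raises the risk of becoming a case is a question about cases against controls. The exposure therefore has to be measured in the same way in both groups. As written, a case mother is asked for a document and, if not recently tested, offered a test. A control mother is covered only by a Table VI item with no stated source. The Protocol introduces the active step because card results do not otherwise reach the study record, and it calls maternal status critical for judging the child's exposure. By that reasoning, controls lack information that cases have.

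A new test also gives the mother's current status, whereas Table VI asks about pregnancy. For a child of up to 59 months the two can differ, and only case mothers can gain a positive result by this route.

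This is a matter of data collection and not something an analysis plan can supply later. Table VII gives controls only a screening and an enrollment contact, and section 4.4.3 provides later contact only to return results. Status not sought at enrollment cannot readily be recovered.

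**Working it through.** **Plan's own figure.** The Protocol gives no figure for maternal HIV exposure. The nearest is the vitamin D illustration in section 6.3.3: 30% exposed among cases, odds ratio 2.0, over 95% power at each site. The implied control prevalence comes from odds (0.30/0.70)/2 = 0.214, that is 17.65%. With 500 per group (the smallest site target) and two-sided alpha 0.01, power is 97.9%, so the figure reproduces. It is not in dispute, and high power gives no protection against bias.

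**Inputs from the Protocol.** Maternal HIV prevalence is one-third in Soweto (taken as 0.33) and 0.19 among antenatal attenders in Lusaka (section 3.2). Targets are 1200 cases and 800 community controls at Soweto, and 800 and 850 at Lusaka (Table XIV).

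**Assumptions.** The Protocol gives no ascertainment rates. Assume that 95-98% of HIV-positive case mothers and 70-90% of HIV-positive control mothers are identified, that no mother is falsely recorded as positive, and that the true odds ratio is 1.0.

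**Scenario A: unknown counted as unexposed.** Let odds(x) = x/(1-x). Then

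observed OR = odds(p × Se_case) / odds(p × Se_control).

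For p = 0.33, Se_case = 0.98 and Se_control = 0.80: odds(0.3234) = 0.478, odds(0.264) = 0.359, and the ratio is 1.33.

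| Prevalence | Case ascertainment | Controls 90% | Controls 80% | Controls 70% |
|---|---|---|---|---|
| 33% | 95% | 1.08 | 1.27 | 1.52 |
| 33% | 98% | 1.13 | 1.33 | 1.59 |
| 19% | 95% | 1.07 | 1.23 | 1.44 |
| 19% | 98% | 1.11 | 1.28 | 1.49 |

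As a limiting case, take case mothers fully ascertained and control mothers at 80%. The observed odds ratio is then 1.38 at Soweto (p = 1/3) and 1.31 at Lusaka. With the site targets and two-sided alpha 0.01, the chance of a significant result under a true odds ratio of 1.0 is 73% and 30%.

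**Scenario B: unknown dropped.** Let status be known for all case mothers, for a fraction f1 of HIV-positive control mothers and for a fraction f0 of HIV-negative control mothers. The odds among the remaining controls are odds(p) × f1/f0, so the observed OR = f0/f1 at any prevalence.

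- f1 = 0.8, f0 = 0.8: 1.00
- f1 = 0.9, f0 = 0.7: 0.78
- f1 = 0.7, f0 = 0.9: 1.29

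The direction depends on which control mothers are unknown. With equal ascertainment in both groups and the same handling of unknowns, a true odds ratio of 1.0 is observed as 1.0.

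**The case against.** The strongest reply is that controls are planned to have this variable. Table VI lists it, section 4.2.2.3 says risk factors are collected from each case and control, section 4.4.2 says the information is the same, and routine antenatal testing means a common source may exist. This stands in part: the gap may be narrower than the illustration suggests. But no source is fixed for controls, record review is optional, and the active step is written for case mothers alone.

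Second, control children have their own HIV antibody test, with PCR if positive at about 18 months or younger. Section 6.3.1 expects half of cases at 1-11 months and 30% at 12-23 months, and controls are frequency matched on age. This also stands in part, and the illustration gives no credit for it. However, parents may decline the test, and the antibody and PCR pair does not serve older children.

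Third, the absence of a maternal test from Tables VII, VIII and X proves little, because the corresponding case tables (III, V and IX) list none either. That is right. The point rests on the text of section 4.2.2.1 and on the lack of any counterpart in the control sections.

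Fourth, a reader might infer that the odds ratio is bound to be biased upward. The documents do not support that. They do not say that unknown mothers are coded as unexposed, a rule commonly left to the statistical analysis plan, and section 4.6 speaks of imputing missing data, though mainly for specimens. The assumed 95-98% in cases is also uncertain, since maternal testing is voluntary and linkage needs consent.

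**Conclusion.** The point holds as a design asymmetry. At two sites an exposure meant for a case-control comparison has an active ascertainment step in one group only, and this conflicts with the statement in section 4.4.2. The odds ratio for HIV exposure is open to differential ascertainment bias. The bias is upward if unknown is treated as unexposed: about 1.27-1.33 at Soweto and 1.23-1.28 at Lusaka for a true value of 1.0, with control ascertainment at 80%. If unknowns are dropped, it ran from 0.78 to 1.29 in the examples tried. These sizes rest on assumed ascertainment rates and are illustrations, not estimates.

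The scope is limited to community controls at South Africa and Zambia; the controls recruited from patient support centers are themselves HIV-infected. A reader might also infer that the etiology comparison is contaminated. The Protocol does not support this, because sections 6.3 and 6.3.1 plan subgroup and stratified analyses by HIV status, meaning infection, and none by HIV exposure.

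**What to change.** In sections 4.2.2.1 and 4.4:

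- Request the same documentation (child health card or antenatal result) from mothers of cases and of community controls at both sites.
- State that the case-control analysis of HIV exposure uses only sources obtained identically in both groups: this documentation, plus the child's antibody and PCR results at 18 months or younger.
- Code undocumented status as unknown, not as unexposed.
- Use newly offered maternal test results only in within-case analyses (severity and etiology among cases), unless control mothers receive the same offer.

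The cost is one document check on the control form at two sites and a short analysis statement, with consent to link the result and the IRB amendment that section 8.2 requires for an added procedure. The downside is somewhat more children of unknown exposure in the case-control comparison. Section 2.3 plans enrollment to end in April 2013 and this version is dated November 2013. Where control enrollment has already closed, the analysis restriction and the coding rule can still be adopted.
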